2.1 Testing hierarchy

To control the FWER of the analysis of the pre-specified primary and key secondary endpoints at the 5% significance level, the hierarchical testing procedure illustrated in [Panel 5](#) has been defined. The test of the null hypotheses will be based on the pre-specified main analysis of the primary estimands. The initial weight allocated to each hypothesis test is specified in [Panel 5](#). Initially, 100% of the weight is allocated to the hypothesis test of the primary endpoint. If the null hypothesis associated with the primary endpoint is rejected, the key secondary endpoint will be assessed.

Panel 5. Hierarchical testing procedure to control the FWER for the pre-specified primary and key secondary endpoints

Abbreviations: FWER = familywise error rate; PASI = Psoriasis Area and Severity Index; PASI 100 = 100% improvement from baseline in PASI score; TTPASI100 = time to PASI 100.

2.2 Statistical hypotheses

The primary and key secondary endpoints for this trial are having PASI 100 response at Week 16 and the time from randomisation to PASI 100 response. Denoting the Week 16 response rates by π and the sub-distribution hazard rates for having PASI 100 response at time t , measured in weeks, by $\lambda(t)$, the null hypothesis for the primary endpoint,

THIS DOCUMENT CONTAINS CONFIDENTIAL INFORMATION AND MUST NOT BE COPIED OR MADE AVAILABLE TO ANY THIRD PARTY WITHOUT THE PRIOR WRITTEN CONSENT OF THE LEO PHARMA GROUP

$$H_0: \pi_{\text{broda}} - \pi_{\text{gus}} \leq 0,$$

will be tested versus the 1-sided alternative,

$$H_1: \pi_{\text{broda}} - \pi_{\text{gus}} > 0,$$

while, for the key secondary endpoint, the null hypothesis,

$$H_0: \lambda_{\text{broda}}(t) = \lambda_{\text{gus}}(t), \text{ for all } t \in (0, 28),$$

will be tested versus the alternative,

$$H_1: \lambda_{\text{broda}}(t) \neq \lambda_{\text{gus}}(t), \text{ for some } t \in (0, 28).$$

3 Sample size

Sample size documentation is provided in the CTP Section 14.1.

4 Trial analysis sets

All screened subjects will be accounted for in the CTR. For the purposes of analysis, the following analysis sets are defined:

Panel 6: Trial analysis sets

Trial analysis set	Description
Intention-to-treat (ITT) analysis set	All randomised subjects. Subjects will be included in the analyses according to the planned (randomised) treatment.
Full analysis set (FAS)	All randomised subjects with at least 1 post-baseline PASI assessment. Subjects will be included in the analyses according to the planned (randomised) treatment.
Safety analysis set (SAF)	All subjects who received IMP. Subjects will be included in the analyses according to the treatment they actually received.

Abbreviations: FAS = full analysis set; IMP = investigational medicinal product; ITT = intention-to-treat; PASI = Psoriasis Area and Severity Index; SAF = safety analysis set.

The ITT analysis set is used for presenting disposition of subjects, demographics and other baseline characteristics. The FAS is used to analyse endpoints and assessments related to the efficacy objectives, and the SAF is used to analyse the endpoints and assessments related to safety.

THIS DOCUMENT CONTAINS CONFIDENTIAL INFORMATION AND MUST NOT BE COPIED OR MADE AVAILABLE TO ANY THIRD PARTY WITHOUT THE PRIOR WRITTEN CONSENT OF THE LEO PHARMA GROUP

Analyses of endpoints based on PP-PASI or PP-IGA will be based on the FAS restricted to those subjects who have a positive PP-PASI score at baseline. Analyses of endpoints based on sPGA-G will be based on the FAS restricted to those subjects who have a positive sPGA-G value at baseline.

Exclusions from the FAS can be considered in special cases as described in ICH E9, Section 5.2.1., Full Analysis Set. If it is decided to exclude a randomised subject from the FAS, a justification addressing ICH E9 will be given in the analysis set definition document (ASDD).

5 Statistical analysis

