7.2 Number of subjects needed

This trial will be conducted at approximately 75 sites in Europe.

Assuming a screening failure of 18%, approximately 293 subjects will be screened, and 240 eligible subjects will be randomised in a 1:1 ratio to treatment with either brodalumab or guselkumab. Randomisation will be stratified by body weight (≤ 100 kg, > 100 kg).

The statistical power considerations for this sample size are described in Section 14.1.

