Panel 20 provides the estimated marginal power for the primary and key secondary endpoints and the conjunctive power for rejecting the null hypotheses associated with the primary and key secondary endpoints, while controlling the familywise error rate (FWER) at the 5% significance level (for 2-sided Fisher's Exact and Gray's tests). The power analysis is based on 100,000 simulations, from the alternating two-state model illustrated in Panel 18, assuming the underlying transition intensities for the brodalumab arm were,

- e) $\lambda_{broda,0,1} = 1.00 \cdot \hat{\lambda}_{broda,0,1} = 0.0333$ and $\lambda_{broda,1,0} = 1.00 \cdot \hat{\lambda}_{broda,1,0} = 0.0272$,
- l) $\lambda_{broda,0,1} = 0.98 \cdot \hat{\lambda}_{broda,0,1} = 0.0326$ and $\lambda_{broda,1,0} = 1.02 \cdot \hat{\lambda}_{broda,1,0} = 0.0277$ or
- u) $\lambda_{broda,0,1} = 1.02 \cdot \hat{\lambda}_{broda,0,1} = 0.0340$ and $\lambda_{broda,1,0} = 0.98 \cdot \hat{\lambda}_{broda,1,0} = 0.0266$,

and assuming the underlying transition intensities for the guselkumab arm were

- e') $\lambda_{gus,0,1} = 1.00 \cdot \hat{\lambda}_{gus,0,1} = 0.0158$ and $\lambda_{gus,1,0} = 1.00 \cdot \hat{\lambda}_{gus,1,0} = 0.0435$,
- l') $\lambda_{gus,0,1} = 0.98 \cdot \hat{\lambda}_{gus,0,1} = 0.0155$ and $\lambda_{gus,1,0} = 1.02 \cdot \hat{\lambda}_{gus,1,0} = 0.0444$ or
- u') $\lambda_{gus,0,1} = 1.02 \cdot \hat{\lambda}_{gus,0,1} = 0.0162$ and $\lambda_{gus,1,0} = 0.98 \cdot \hat{\lambda}_{gus,1,0} = 0.0427$.

THIS DOCUMENT CONTAINS CONFIDENTIAL INFORMATION AND MUST NOT BE COPIED OR MADE AVAILABLE TO ANY THIRD PARTY WITHOUT THE PRIOR WRITTEN CONSENT OF THE LEO PHARMA GROUP

The scenarios described in bullet points l), u), l') and u') have been introduced for robustness of the resulting sample size with respect to small perturbations of the transition intensities.

Panel 20: Estimated conjunctive power for rejecting the hypotheses associated with the primary and key secondary endpoints

Sample size per arm	Scenario for transition intensities				Power for the primary endpoint	Power for the key secondary endpoint	Conjunctive power		
	$\lambda_{\text{broda},0,1}$	$\lambda_{\text{broda},1,0}$	$\lambda_{\text{gus},0,1}$	$\lambda_{\text{gus},1,0}$					
N=110	e)	0.0333	0.0272	e')	0.0158	0.0435	83.3%	96.8%	82.5%
N=110	e)	0.0333	0.0272	l')	0.0155	0.0444	85.3%	97.4%	84.6%
N=110	e)	0.0333	0.0272	u')	0.0162	0.0427	80.9%	95.8%	79.9%
N=110	l)	0.0326	0.0277	e')	0.0158	0.0435	80.7%	95.8%	79.7%

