N=110	l)	0.0326	0.0277	l')	0.0155	0.0444	82.5%	96.4%	81.6%
N=110	l)	0.0326	0.0277	u')	0.0162	0.0427	78.0%	94.7%	76.8%
N=110	u)	0.0340	0.0266	e')	0.0158	0.0435	85.8%	97.5%	85.1%
N=110	u)	0.0340	0.0266	l')	0.0155	0.0444	87.5%	98.0%	86.9%
N=110	u)	0.0340	0.0266	u')	0.0162	0.0427	83.8%	96.9%	83.0%
N=120	e)	0.0333	0.0272	e')	0.0158	0.0435	87.0%	97.8%	86.4%
N=120	e)	0.0333	0.0272	l')	0.0155	0.0444	88.5%	98.3%	88.0%
N=120	e)	0.0333	0.0272	u')	0.0162	0.0427	84.7%	97.1%	84.0%
N=120	l)	0.0326	0.0277	e')	0.0158	0.0435	84.1%	96.9%	83.3%
N=120	l)	0.0326	0.0277	l')	0.0155	0.0444	86.0%	97.6%	85.3%
N=120	l)	0.0326	0.0277	u')	0.0162	0.0427	81.9%	96.2%	81.0%
N=120	u)	0.0340	0.0266	e')	0.0158	0.0435	89.3%	98.4%	88.8%
N=120	u)	0.0340	0.0266	l')	0.0155	0.0444	90.6%	98.7%	90.2%
N=120	u)	0.0340	0.0266	u')	0.0162	0.0427	87.2%	97.9%	86.6%

Abbreviation: N = number of subjects.

THIS DOCUMENT CONTAINS CONFIDENTIAL INFORMATION AND MUST NOT BE COPIED OR MADE AVAILABLE TO ANY THIRD PARTY WITHOUT THE PRIOR WRITTEN CONSENT OF THE LEO PHARMA GROUP

Based on the above assumptions and results, a sample size of 240 subjects would ensure a conjunctive power of at least 80% in order to reject the null hypotheses for both the primary and key secondary endpoints for all of the illustrated scenarios.

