5.3 Intercurrent events

An intercurrent event refers to a post-randomisation event that either precludes the existence of or affects the interpretation of the measurements of an endpoint. For the purposes of this trial, we define the following 3 intercurrent events:

- **Permanent discontinuation of IMP independent of pandemic restrictions:** This event occurs when a subject permanently discontinues IMP for reasons not related to COVID-19 pandemic restrictions. Permanent discontinuation of IMP due to sickness with COVID-19 (an AE) will be interpreted as permanent discontinuation of IMP independent of pandemic restrictions. This event can occur either at the subject's own initiative or at the investigator's or sponsor's discretion.

Derivation of events from data: This event will be taken to have occurred if the data recorded in the 'End of treatment' eCRF form fulfil all of the following.

- 'Has the subject completed the treatment period?' is answered 'No'
- 'Primary reason for permanent discontinuation from IMP?' is not answered 'Death' or 'Lost to follow-up'
- 'Was the decision to permanently discontinue IMP related to COVID-19 pandemic restrictions?' is not answered 'Yes'.

The timing of the event will be taken as the reported 'Date of last administration of IMP'.

- **Permanent discontinuation of IMP due to pandemic restrictions:** This event occurs when a subject permanently discontinues IMP for reasons related to COVID-19 pandemic restrictions. Permanent discontinuation of IMP due to sickness with COVID-19 (an AE) will not be interpreted as permanent discontinuation of IMP due to COVID-19 pandemic restrictions. Examples of permanent discontinuation of IMP due to pandemic restrictions

THIS DOCUMENT CONTAINS CONFIDENTIAL INFORMATION AND MUST NOT BE COPIED OR MADE AVAILABLE TO ANY THIRD PARTY WITHOUT THE PRIOR WRITTEN CONSENT OF THE LEO PHARMA GROUP

are quarantines, travel limitations, subject being unable or unwilling to travel to site due to personal pandemic-related reasons, site closures, reduced availability of site staff, and interruptions to supply chain of IMP.

Derivation of events from data: This event will be taken to have occurred if the data recorded in the ‘End of treatment’ eCRF form fulfil all of the following.

- ‘Has the subject completed the treatment period?’ is answered ‘No’
- ‘Primary reason for permanent discontinuation from IMP?’ is not answered ‘Death’ or ‘Lost to follow-up’

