5.4.1.1 Main analysis

For each of the 250 complete datasets, the treatment effect will be estimated, along with the associated standard error, from a logistic regression model, adjusted for baseline body weight (≤ 100 kg, > 100 kg) and the baseline value of the underlying response variable. Based on Rubin’s rules, a combined estimate and standard error for the treatment effect will be calculated and the associated t statistic will be used for testing the null hypothesis that the response rate for the brodalumab arm is less than or equal to the rate for the guselkumab arm, against the alternative that brodalumab is superior to guselkumab. The statistical test will be based on the odds ratio or, equivalently, on the log-odds ratio as expressed through the treatment coefficient in the logistic regression model. In practice, the t test will be carried out as a two-sided test at the 5% significance level, where the null hypothesis will only be rejected in favour of the stated alternative if the treatment effect estimate is in favour of brodalumab. This corresponds to a one-sided test at the 2.5% significance level.

To quantify the magnitude of the potential treatment effect, estimates of the LS-mean risk difference and odds ratio will be presented along with the associated 95% confidence intervals

THIS DOCUMENT CONTAINS CONFIDENTIAL INFORMATION AND MUST NOT BE COPIED OR MADE AVAILABLE TO ANY THIRD PARTY WITHOUT THE PRIOR WRITTEN CONSENT OF THE LEO PHARMA GROUP

(CIs), based on combining estimates and associated standard errors from the 250 analyses using Rubin's rules.

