14.3.6 Estimand strategy	
Prior TNF-α inhibitor use at baseline ($\leq 1, > 1$) will not be included as a factor in any analysis model. This also means that interactions with prior TNF-α inhibitor use at baseline ($\leq 1, > 1$) will not be included in the sensitivity analysis model described in Section 5.4.1.2.2.
	
Amendment 3 of the CTP introduced changes to the eligibility criteria and handled these changes in the analysis by including prior TNF-α inhibitor use at baseline ($\leq 1, > 1$) as a factor in all analysis models.
 
However, the decision to end the trial ahead of schedule was made shortly after implementing Amendment 3 of the CTP, and very few subjects can be expected to have been randomised under the amended eligibility criteria. In particular, very few randomised subjects can be expected to have used more than one TNF-α inhibitor at baseline, so we do not consider the adjustment for prior TNF-α inhibitor use at baseline ($\leq 1, > 1$) feasible.

THIS DOCUMENT CONTAINS CONFIDENTIAL INFORMATION AND MUST NOT BE COPIED OR MADE AVAILABLE TO ANY THIRD PARTY WITHOUT THE PRIOR WRITTEN CONSENT OF THE LEO PHARMA GROUP

14.3.6 Estimand strategy	In procedures for multiple imputation, the CTP specifies the number of imputations to be 1000. Instead, the number of imputations will be 250.	To align with the number of imputations specified for other brodalumab trials, LP0160-1329 and LP0160-1396. 250 imputations substantially exceed the default number of imputations NIMPUTE=25 for PROC MI, and will for sure exceed the percentages of cases with missing values (described as a rule of thumb for the number of imputations in the SAS/STAT 15.2® User's Guide for PROC MI).
14.3.6.2 Estimand strategy for binary endpoints	The procedures for multiple imputation of missing data have been slightly changed: In case of PASI 100 response at Week 16, the CTP describes part of the procedure as a stepwise imputation of underlying PASI scores, sequentially for Weeks 2, 4, 6, 8, 10, 12, 14, and 16. This stepwise process has been changed to also include imputation of underlying PASI scores for baseline and Week 1. A similar change has been made to the analogous stepwise procedure for imputing underlying IGA values.	To handle instances of missing baseline values, to accommodate the above-described addition of the explorative endpoint 'having PASI 100 response at Week 1' and to make use of the data collected at Week 1 in the imputation of missing data.

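### SAP Section 3 still rests on the 240-subject, 80% power calculation, although SAP Section 6 records that the trial was ended ahead of schedule

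*SAP*

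**What the plan says.** SAP Section 3 is one sentence: "Sample size documentation is provided in the CTP Section 14.1". Protocol Section 14.1 concludes that "a sample size of 240 subjects would ensure a conjunctive power of at least 80" per cent for rejecting both the primary and the key secondary null hypotheses, in all illustrated scenarios. Protocol Section 7.2 gives the matching plan: "240 eligible subjects will be randomised in a 1:1 ratio to treatment with either brodalumab or guselkumab".

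SAP Section 6 (Panel 22) gives the later position: "the decision to end the trial ahead of schedule was made shortly after implementing Amendment 3 of the CTP". It adds that very few subjects are expected to have entered under the amended criteria. The early end is then the reason for removing the prior TNF-α inhibitor factor from every model and for dropping the retrieved-data pattern-mixture sensitivity analysis. No entry in Panel 22 concerns sample size or power. The testing hierarchy and hypotheses (SAP Sections 2.1 and 2.2) and the main tests (Sections 5.4.1.1 and 5.4.2.1) are kept as confirmatory.

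**The concern.** The SAP was written after the blind review and before unblinding (SAP Section 1). Its authors therefore knew of the early end and could have known how many subjects had been randomised. They carried the early end through to the models but not to the sample size section. A reader of the SAP is left with a design power above 80% as the only yardstick.

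What is at stake is how a non-significant primary result is read. Set against a trial said to have at least 80% power, it looks like fair evidence that the assumed difference is absent. Set against a much smaller trial, it says little. The hierarchy also stops if the primary test fails, so lower primary power reduces the chance that the key secondary endpoint is formally tested at all.

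**Working it through.** **1. Is the trial smaller than 240?** Neither document states the number randomised. (The SAP's design schematic, Panel 3, lists N among its abbreviations, but the drawing is not in the public text.) These statements bear on it:

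- Amendment 3 (10-Mar-2022) cut the target from 260 to 240 and eased eligibility to help recruitment, so the target had not been reached.
- The decision to end came shortly afterwards, with very few subjects expected under the new criteria.
- Protocol Appendix 3I describes the ordinary stop as reaching the requested number. Ending ahead of schedule is a different thing.

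A number below 240 is an inference, but a strong one. Its size is unknown.

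**2. Inputs** (Protocol Section 14.1). Allocation is 1:1. Power was computed for two-sided Fisher's exact and Gray's tests, "while controlling the familywise error rate (FWER) at the 5% significance level". Weekly transition intensities (into response, out of response) are:

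- Base case e/e': brodalumab 0.0333, 0.0272; guselkumab 0.0158, 0.0435.
- Least favourable case l/u': brodalumab 0.0326, 0.0277; guselkumab 0.0162, 0.0427.

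**3. Week 16 rates** from the protocol's formula, π(16) = λ01/(λ01+λ10) × [1 − exp(−16(λ01+λ10))]:

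- e/e' brodalumab: 0.0333/0.0605 × [1 − exp(−0.968)] = 0.5504 × 0.6202 = 34.1%.
- e/e' guselkumab: 0.0158/0.0593 × [1 − exp(−0.9488)] = 0.2664 × 0.6128 = 16.3%. The difference is 17.8 points.
- l/u': 33.5% and 16.8% by the same steps.

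**4. Reproducing Panel 20 at 120 per arm.** Primary power is by exact enumeration of Fisher's test. Conjunctive power is by simulating the two-state process at the scheduled visits, with a log-rank test on first observed PASI 100. Log-rank equals Gray's test here because the planning model has no competing event.

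- e/e': primary 86.9% (stated 87.0%), conjunctive 86.1% (stated 86.4%).
- l/u': primary 81.9% (stated 81.9%), conjunctive 81.4% (stated 81.0%).

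All nine scenarios reproduce, so Section 14.1 is right for 240.

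**5. The same calculation at smaller assumed numbers.** The CI half-width for the risk difference (base case, unadjusted) is 1.96 × √[(0.3413×0.6587 + 0.1633×0.8367)/n] = 1.96 × √(0.36145/n).

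| Per arm (total) | Primary e/e', l/u' | Conjunctive e/e', l/u' | CI half-width, points |
|---|---|---|---|
| 120 (240) | 86.9%, 81.9% | 86%, 81% | 10.8 |
| 110 (220) | 83.4%, 78.0% | 83%, 77% | 11.2 |
| 100 (200) | 79.2%, 73.4% | 78%, 72% | 11.8 |
| 80 (160) | 68.8%, 62.6% | 68%, 60% | 13.2 |
| 60 (120) | 53.7%, 47.9% | 51%, 44% | 15.2 |
| 40 (80) | 36.5%, 32.1% | 32%, 28% | 18.6 |

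Panel 20 itself prints 76.8% conjunctive power at 110 per arm for l/u'. On this basis the all-scenarios 80% statement needs about 117 to 118 per arm (l/u': 79.5% at 116, 79.9% at 117, 80.4% at 118).

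**6. Dependence on the test.** The SAP's primary test is a t test on the logistic treatment coefficient, of which it says: "This corresponds to a one-sided test at the 2.5% significance level". Fisher's test is more conservative. With an unadjusted logistic Wald test, base-case conjunctive power is 89%, 82%, 72%, 57% and 39% at 120, 100, 80, 60 and 40 per arm. In the l/u' case it stays near 80% down to about 106 per arm. The level shifts up by a few points, but the decline remains.

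**The case against.** Section 14.1 is a design-stage calculation, and the SAP says only that the documentation is there, which is true. Section 6 is headed as a list of changes to analyses, and sample size is not an analysis. The clinical trial report will give the number randomised (SAP Section 7.1), and 95% CIs for the risk difference and odds ratio are already planned, so imprecision will be visible. No test depends on reaching 240, and neither document treats non-significance as equal efficacy.

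Most of this stands. It makes the point a disclosure gap and not a calculation error, and it limits the severity. It does not answer the matter of timing: a statement on how a null result will be read carries more weight before unblinding than after. Nor is this a request for observed power. It asks for power at the achieved number under effects fixed in advance.

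A reader might also infer more from SAP Section 5.3, which says of discontinuation independent of pandemic restrictions: "This event can occur either at the subject's own initiative or at the investigator's or sponsor's discretion". The tempting reading is that subjects taken off treatment because the sponsor closed the trial would be scored as failures. The documents do not support it:

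- Nothing says that anyone was taken off treatment for that reason.
- The wording was already in Protocol Section 14.3.6.1 and fits the subject-level stopping in Protocol Section 10.1.
- Blind review found only administrative censoring (Panel 22), which SAP Section 5.4.2.1 ties to trial completion. This does not strictly exclude closure-driven stops, which would be competing events, but it fits a halt to recruitment with follow-up completed.
- From Amendment 3 to the SAP (02-Feb-2023) is 329 days, or 47 weeks, against about 32 weeks of participation.

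Changing the rule would also redefine an intercurrent event of the primary estimand after blind review, for a case not shown to exist.

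**Conclusion.** The point holds, at moderate severity. The SAP's only statement on size and power describes a trial of 240 that was almost certainly not completed, and the SAP itself records why. Panel 20 has little slack in its least favourable scenario: on its own Fisher basis, a shortfall of 3 or 4 per arm takes that row below 80%. The planned logistic test tolerates a larger shortfall. At 40 per arm the CI half-width (18.6 points) exceeds the planned difference (17.8), so an estimate equal to the plan would not exclude zero.

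This rests on the inference that fewer than 240 were randomised, on Panel 20's assumed effects, on 1:1 allocation, and on a planning model without discontinuation. A reader might go further and conclude that Section 14.1 is miscalculated, that a particular power was lost, or that type I error is affected. The first is wrong, since the figures reproduce. The second cannot be known without the number randomised. For the third, the reason for ending is not given, no interim analysis was planned (SAP Section 5.7), and nothing in the documents points to it.

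**What to change.** Before unblinding, revise SAP Section 3 and add an entry to Section 6 (Panel 22) to:

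- state the number randomised;
- say that recruitment ended before 240, if that is so, and that the 240-subject, 80% power statement no longer applies;
- restate primary and conjunctive power at that number under the Panel 20 scenarios, naming the test used, with the expected 95% CI width for the risk difference;
- say that a non-significant result will not be read as evidence of equal efficacy.

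The tests, estimands and hierarchy stay as they are. The cost is a few sentences, a short calculation and a less favourable stated power. No further subjects are needed.

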5.1 General principles

Unless otherwise specified, significance tests will be two-sided using the 5% significance level. All confidence intervals will be presented with 95% degree of confidence, unless otherwise specified. Least squares (LS)-mean estimates will be based on the observed margins.

Inference based on multiple imputation methods will consist of n=250 imputed datasets to ensure that the between-imputation variance is estimated with adequate precision. For the analysis of binary endpoints relying on multiple imputation methods to address missing data, the risk differences and log odds ratios along with the associated standard errors will be pooled directly based on Rubin's rules to quantify the potential treatment benefit. For the analysis of multiply-imputed datasets using analysis of covariance (ANCOVA), the estimated regression coefficients and associated standard errors will be pooled directly using Rubin's rules.

Tabulations of data by visit will explicitly account for missing data. Categorical data will be summarised using the number and percentage of subjects in each category and treatment group. Continuous data will be summarised using the mean, SD, median, minimum, and maximum values.

Efficacy assessments will be summarised numerically and graphically by protocol defined visit week for the two treatment groups. The summarisation will be done based on all observed data, as well as with data collected after occurrence of intercurrent events excluded. Continuous efficacy data will be graphically summarised using spaghetti plots, where individual subject trajectories and mean trajectories will be plotted by connecting subsequent non-missing values by straight lines. Categorical efficacy data will be summarised using stacked bar charts, where

THIS DOCUMENT CONTAINS CONFIDENTIAL INFORMATION AND MUST NOT BE COPIED OR MADE AVAILABLE TO ANY THIRD PARTY WITHOUT THE PRIOR WRITTEN CONSENT OF THE LEO PHARMA GROUP

missing data will be explicitly accounted for by being represented on the plot as a separate category.

For each combination of protocol defined visit week (16 and 28) and treatment group, the percent change from baseline in PASI will be presented using a waterfall plot, representing subject-specific values as bars plotted in descending order. The plot will represent subjects with missing values as dots (or equivalent) and use a colouring scheme for highlighting bars corresponding to subjects who have experienced intercurrent events prior to the time of endpoint assessment.

For analysis of non-daily assessments, the baseline assessment is defined as the latest available assessment at or prior to the baseline visit (Visit 2; Week 0). For analysis of the daily pruritus and pain NRS assessments, nominal Days are defined as relative days starting with the randomization date as Day 1. The Day value is incremented by 1 for each date following the randomization date. Dates prior to the randomization date are decremented by 1, with the date preceding the randomization date designated as Day -1 (there is no Day 0). With this designation of Days, nominal Week q is defined as starting on Day $7 \cdot q - 7$ and ending on Day $7 \cdot q - 1$ for non-positive integers q and starting on Day $7 \cdot q - 6$ and ending on Day $7 \cdot q$ for positive integers q . **Panel 7** explicitly describes selected nominal weeks for the analysis of daily pruritus and pain NRS assessments.

Panel 7. Selected nominal weeks for the analysis of pruritus and pain NRS assessments

Week (nominal weeks)	Start of the week	End of the week
Week 0	Day -7	Day -1
Week 1	Day 1	Day 7
Week 4	Day 22	Day 28
Week 8	Day 50	Day 56
Week 16	Day 106	Day 112
Week 28	Day 190	Day 196

THIS DOCUMENT CONTAINS CONFIDENTIAL INFORMATION AND MUST NOT BE COPIED OR MADE AVAILABLE TO ANY THIRD PARTY WITHOUT THE PRIOR WRITTEN CONSENT OF THE LEO PHARMA GROUP

Calculation of a pruritus or pain NRS weekly average requires available data to have been recorded on at least 4 days within the given week – otherwise the weekly average will be considered missing. The baseline weekly average is defined as the latest available weekly average at or prior to Week 0.

In case of differences between the IRT and the eCRF in recorded values of the stratification factor, baseline body weight (≤ 100 kg, > 100 kg), the value recorded in the eCRF will be used for analysis.

Handling of missing values and imputation

Likelihood methods, as well as single and multiple imputation methods will be implemented to account for the presence of missing data and to address occurrences of intercurrent events by ‘hypothetical’ strategies in the statistical analysis of the primary and secondary endpoints. For imputation-based methods, non-monotone missing data will be imputed based on a Markov Chain Monte Carlo method, assuming an underlying multi-variate normal distribution for continuous endpoints and the fully-conditional specification method for binary or ordinal endpoints. For imputation-based methods, monotone missing data will be imputed based on a monotone regression method for continuous endpoints and a fully-conditional specification logistic regression method for binary or ordinal endpoints. The variables used in the analysis model will be included in the imputation model. Here, the categorization into non-monotone and monotone missing data-patterns is based on all scheduled visits.

The ‘delta-adjusted’ pattern-mixture model provides a convenient framework for assessing the impact of departures from the missing at random (MAR) assumption in instances where the ‘control-based’ pattern-mixture model is not reasonable, e.g. when comparing 2 active treatments. For continuous endpoints, the ‘delta-adjusted’ pattern-mixture model assumes that within a given treatment arm, the mean response value among withdrawn subjects differs from the mean response among subjects remaining in the trial by a specified margin, denoted by Δ . For a given treatment arm at a specific timepoint, missing data are imputed based on the distribution of the conditional mean fitted to the observed data adjusted by the specified margin, Δ . When imputing missing ordinal data in the context of a logistic regression model, Δ is interpreted as the odds ratio of a given level on the logarithmic scale for withdrawals vs. completers.

THIS DOCUMENT CONTAINS CONFIDENTIAL INFORMATION AND MUST NOT BE COPIED OR MADE AVAILABLE TO ANY THIRD PARTY WITHOUT THE PRIOR WRITTEN CONSENT OF THE LEO PHARMA GROUP

